## 7.3 Follow-up of adverse events

All AEs will be followed until they have abated, or until a stable situation has been reached. Depending on the event, follow up may require additional tests or medical procedures as indicated, and/or referral to the general physician or a medical specialist. SAEs need to be reported till end of study within the Netherlands and Belgium, as defined in the protocol

## 7.4 Data Safety Monitoring Board (DSMB) / Safety Committee]

This study adds a moderate risk ("matige kans") of moderate to slight to moderate damage ("milde tot matige schade") and small risk ("kleine kans") of severe damage ("ernstige schade"), consequently adding a moderate risk ("matig risico") according to the risk classification of the "Nederlandse Federatie van Universitair Medische Centra" (NFU). Continuous safety monitoring will be performed accordingly.

An independent data safety monitoring board (DSMB) will be installed to perform ongoing safety surveillance as described in the charter for the Data Safety Monitoring Committee, attached as a supplement in section K5. Also, resumes of the members of the DSMB are attached in this section. The DSMB will decide on safety and continuation of the study. The DSMB will evaluate the study data and advise the sub-investigator on the continuing safety of current participants and those yet to be recruited, as well as the continuing validity and scientific merit of the trial. The members of the DSMB have no conflict of interest, are not involved in the study, nor are they receiving funds. The DSMB will have full access to the study data.

A planned interim safety analysis will be performed after inclusion of 130 and 260 patients. The DSMB will analyze all cases in which complications graded as grade IIIb or higher on the Clavien-Dindo scale have occurred (Table 1). Criteria for terminating the study is when patients undergoing the intervention, are at an increased risk of developing severe complications with prolonged negative impact on patients health, that is higher than expected based on literature or disproportional to the potential benefit of the operation. The advice(s) of the DSMB will only be sent to the sponsor of the study. Should the sponsor decide not to fully implement the advice of the DSMB, the sponsor will send the advice to the reviewing METC, including a note to substantiate why (part of) the advice of the DSMB will not be followed.

Table 1. Clavien-Dindo scale

Grade I	Any deviation from the normal post-operative course not requiring surgical, endoscopic or radiological intervention. This includes the need for certain drugs (e.g. antiemetics, antipyretics, analgesics, diuretics and electrolytes), treatment with physiotherapy and wound infections that are opened at the bedside
Grade II	Complications requiring drug treatments other than those allowed for Grade I complications; this includes blood transfusion and total parenteral nutrition (TPN)
Grade III	Complications requiring surgical, endoscopic or radiological intervention  Grade IIIa - intervention not under general anaesthetic  Grade IIIb - intervention under general anaesthetic
Grade IV	Life-threatening complications; this includes CNS complications (e.g. brain haemorrhage, ischaemic stroke, subarachnoid haemorrhage) which require intensive care, but excludes transient ischaemic attacks (TIAs)  Grade IVa - single-organ dysfunction (including dialysis)  Grade IVb - multi-organ dysfuncton
Grade V	Death of the patient

#### 8. STATISTICAL ANALYSIS

Data will be analyzed according to the intention-to-treat principle. The primary outcome (difference in incidence of recurrence between groups) will be analyzed using multivariate cox-regression to account for the stratification variables, i.e. first episode vs. recurrent cases; and operating center. Results will graphically be presented using Kaplan-Meier curve.

Surgical findings, and complications in the operative group will be assessed descriptively in a quantitative analysis. Quality of life, gastro-intestinal complaints, healthcare and societal costs will be analyzed using mixed-effect models. Differences with a P-value <0.05 are considered statistically significant.

In case of loss to follow-up, cases are included in survival analysis up to the moment of loss to follow-up. The main potential intercurrent event is abdominal surgery for an indication unrelated to ASBO during follow-up. After this new surgery new adhesions might form that could interfere with the risk of developing an ASBO. Within the 2 year time frame, such unrelated reoperations are expected in approximately 5% of patients. Because of the randomization, we expect both groups to be at equally risk for such event. Our main analysis will be on intention to treat basis, and for this analysis, data from patients with this intercurrent event will be further collected and analysis. As a secondary outcome we will also analysis the data per protocol, in which case patients with intercurrent events are censored.

Another potential intercurrent event is cross-over from the control to intervention group of patients after a recurrence. Patients that cross-over have already reached the primary outcome of a recurrence, and thus this event has no impact on the primary outcome. However, it might impact some of the secondary outcomes. This will be recorded, and accounted for in the secondary analyses.

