## aSBO Adhesive Small Bowel Obstruction

#### **SUMMARY**

Rationale: Adhesive small bowel obstruction (aSBO) is a frequent surgical emergency, associated with 3-8% hospital mortality and a high risk of recurrence (20% at two years of follow-up). ASBO can be treated conservatively or by emergency surgery. In the absence of bowel ischemia or strangulation, conservative treatment is often preferred, to avoid the excess morbidity and mortality from emergency surgery. Recent epidemiological studies, however, demonstrate a considerable higher recurrence risk of aSBO after conservative treatment that is associated with hospital readmissions and lower survival. Elective adhesiolysis following successful conservative treatment might reduce these long-term risks whilst avoiding the high complication rate of emergency surgery.

**Objective**: We aim to investigate the efficacy of elective adhesiolysis following conservative treatment for aSBO as compared to the current state of the art (wait-and-see policy) to prevent long-term recurrence of aSBO. Further we will evaluate quality of life, healthcare and societal costs.

**Study design:** Multicenter open-label randomized controlled trial, including 380 patients. **Study population:** Adult patients who recovered from aSBO by conservative treatment. Patients that are inoperable for medical, anaesthesiological or surgical reasons are excluded. **Intervention (if applicable)**: The intervention of investigation is elective adhesiolysis. Adhesiolysis is an abdominal procedure in which all adhesions are cut, and adhesion prevention applied to reduce the risk of adhesion reformation. The intervention is compared to wait-and-see policy (the current standard treatment)

**Main study parameters/endpoints:** Primary outcome is recurrence, defined as readmission for obstructive systems with aetiology of adhesions confirmed by CT. We hypothesize a 50% reduction in recurrence in the intervention arm. Secondary outcomes are morbidity from surgery, health-related quality of life (EQ5D), healthcare costs and societal costs (iMCQ and iPCQ)

Nature and extent of the burden and risks associated with participation, benefit and group relatedness:

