surgery.(14) In this study 122 patients with chronic complaints from adhesions were included, of whom 60 had previous episodes of aSBO. In both the entire cohort and the subgroup of patients with previous aSBO, elective adhesiolysis resulted in a significant 3-fold reduction in incidence of aSBO during 5-year follow-up.

The aim of the present study is to assess the efficacy and safety of elective adhesiolysis to reduce long-term recurrence of aSBO, as compared to a wait-and-see policy. Primary outcome is the 2-year risk of readmission for recurrence, secondary outcomes are chronic abdominal complaints, mortality, operative morbidity, quality of life, and healthcare and societal costs (measured by iMCQ and iPCQ). In the selection of outcomes we made sure to incorporate the outcomes from the ASBO core outcome set that a relevant for long-term evaluation.(15)

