## 2. OBJECTIVES

## **Primary Objective:**

To assess the efficacy and safety of elective adhesiolysis with application of adhesion barrier to prevent recurrence of aSBO as compared to wait-and-see.

Recurrence is defined as a hospital readmission for symptoms of bowel obstruction, after exclusion of other causes of bowel obstruction by CT (see outcomes).

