## 6.1.2 Secondary study parameters/endpoints (if applicable)

Secondary outcomes are:

- Recurrence at 5 year (identified by record linking[BE] or general practitioner data[NL])
- Recurrences needing surgery
- Recurrence risks stratified by patients and surgical characteristics (Sex, age)
- Recurrence risk in the operative subgroup stratified for laparoscopic vs open surgery
- Morbidity from elective adhesiolysis:
  - Serious adverse events and complications, graded by Clavien-Dindo score.
  - Intra-operative events (i.e. bowel injury), graded by ClassIntra®

- ICU admission
- Reinterventions within 90 days

Patient questionnaires at 1 and 2 years of follow-up

- Health-related quality of life measured by EQ5D
- Gastro-intestinal related quality of life measured by GIQLI
- Characteristics of abdominal pain
- Costs from healthcare perspective (measured by modified iMCQ)
- Costs from societal perspective (measured by modified iMCQ and iPCQ)
- Cost-effectiveness (incremental cost-effectiveness ratio, i.e. cost per QALY) Surgical follow-up
- History taking with focus on potential recurrences
  - Review of data from readmission in same hospital
  - Ask patients if there have been readmission to other hospitals
- Assessment of complaints related to obstruction
  - Chronic or recurrent nausea, bloating, abdominal pain
  - Unintended weight loss
- Physical examination focused on abdominal pain and incisional hernia

The full iMCQ and iPCQ questionnaires are quite extensive and elaborate for patients to fill out. Therefore a modified version of these questionnaires is applied, in which only the domains that are potentially affected by ASBO are included, as decided upon during an expert meeting with healthcare professionals and patient representatives. This method is frequently applied in cost-effectiveness research and also increases the number of patients completing the questionnaire.

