#### 7.2.2 Serious adverse events (SAEs)

A serious adverse event is any untoward medical occurrence or effect that

- results in death;
- is life threatening (at the time of the event);
- requires hospitalisation or prolongation of existing inpatients' hospitalisation;
- results in persistent or significant disability or incapacity;
- is a congenital anomaly or birth defect; or
- any other important medical event that did not result in any of the outcomes listed above due to medical or surgical intervention but could have been based upon appropriate judgement by the investigator.

An elective hospital admission will not be considered as a serious adverse event.

All SAEs as defined in the protocol must be reported to the Sponsor within 24 hours of the trial staff becoming aware of the event. The sponsor will report the SAEs occurring up to 3 months following treatment through the web portal *ToetsingOnline* to the accredited METC that approved the protocol [NL] and the approving ethical Commission in Belgium. SAEs that result in death or are life threatening will be reported as soon as possible after becoming aware, followed by a period of maximum of 8 days to complete the initial preliminary report. All other SAEs will be reported within a period of maximum 15 days after the sponsor has first knowledge of the serious adverse events. In Belgium all other SAEs will reported as part of the yearly progress report.

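### The primary objective promises safety compared with wait-and-see, but the protocol plans to analyse complications only in operated patients and drops mortality from its endpoint list

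*Protocol*

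**What the plan says.** The primary objective in Section 2 reads: "To assess the efficacy and safety of elective adhesiolysis with application of adhesion barrier to prevent recurrence of aSBO as compared to wait-and-see". Section 1 gives the same aim, to "assess the efficacy and safety of elective adhesiolysis to reduce long-term recurrence of aSBO, as compared to a wait-and-see policy". In both places safety is stated as a comparison.

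Section 1 then says that "secondary outcomes are chronic abdominal complaints, mortality, operative morbidity, quality of life, and healthcare and societal costs". The formal list in Section 6.1.2 puts harm under "Morbidity from elective adhesiolysis", with the item "Serious adverse events and complications, graded by Clavien-Dindo score", and also names intra-operative events, ICU admission and reinterventions inside 90 days. It does not name mortality. Nor do the secondary objectives in Section 2 or the Summary, which reads "Secondary outcomes are morbidity from surgery, health-related quality of life (EQ5D), healthcare costs and societal costs (iMCQ and iPCQ".

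On analysis, Section 8 says: "Surgical findings, and complications in the operative group will be assessed descriptively in a quantitative analysis". Section 8.2 covers per-protocol recurrence, quality of life, gastro-intestinal complaints and costs. It contains no analysis of complications, serious adverse events (SAEs) or deaths.

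Data collection is broader than this. Section 7.2.1 records adverse events in any subject, related to treatment or not. Section 7.2.2 counts death as an SAE, and Section 7.3 requires SAEs to be reported until the study ends. Table 1 of study procedures schedules visits at 6, 12 and 24 months for both arms and limits only visits 2 to 4 to the intervention arm.

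**The concern.** The argument for elective surgery is a trade: accept planned operative harm now to avoid harm from recurrence later. The protocol itself ties recurrence to readmission, reintervention and higher long-term mortality (Summary, Section 9.4). A description of complications in operated patients counts one side of that trade. Complications, ICU stays and deaths after a recurrence under wait-and-see are the other side, and no safety analysis is stated for them.

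This is more than detail left to a statistical analysis plan. Section 8 fixes a one-arm description, and an analysis plan that follows it would inherit the mismatch with Section 2. For mortality the protocol contradicts itself: an outcome declared in Section 1 is missing from the list meant to define the outcomes.

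**Working it through.** **1. The places side by side**

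| Place | What it says on harm | Patients covered |
|---|---|---|
| Section 1 and Section 2, primary objective | Safety against wait-and-see | Both arms |
| Section 1, outcomes | Mortality and operative morbidity | Mortality: not restricted |
| Summary | Morbidity from surgery | Operated |
| 6.1.2 | Morbidity of the operation; mortality not named | Operated |
| 6.1.2 | Recurrence leading to surgery | Both arms |
| 8 | Complications, descriptive | Operative group |
| 8.2 | No analysis of harm | None |
| 8.2, economic evaluation | Costs and QALYs by intention to treat | Both arms |
| 7.2.1, 7.2.2, 7.3 | Adverse events and SAEs, including death, to end of study | All subjects |

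The comparison in the objective and the data collection agree with each other. The endpoint list and the stated analysis do not match them.

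**2. What the sample size covers (Section 4.4)**

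Inputs: 20% against 10% recurrence at two years, two-sided alpha 0.05, power 80%, 378 patients.

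- HR = ln(0.90)/ln(0.80) = 0.472.
- Events by Schoenfeld at HR 0.47 = 4 × (1.960 + 0.842)² / (ln 0.47)² = 55.1, rounded up to 56.
- Patients = 56 / 0.15 = 373.3, that is 374, within 3% of the stated 378. Power at 378 × 0.15 = 56.7 events is about 81%.

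The plan's figure reproduces. It concerns recurrence only; no figure is given for safety.

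**3. Size of the trade on the plan's own figures**

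Assume 190 per arm and that everyone allocated to surgery is operated on.

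- Recurrences: 190 × 0.20 = 38 against 190 × 0.10 = 19, so 19 fewer. Number needed to treat = 1/0.10 = 10.
- Iatrogenic organ injury at 2–4% (Section 7.2.1): 190 × 0.02 = 3.8 to 190 × 0.04 = 7.6, about 4 to 8 patients, or 0.2 to 0.4 per recurrence avoided.
- Exact 95% intervals: 4/190 gives 0.6–5.3%; 8/190 gives 1.8–8.1%.

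These intervals describe operative risk adequately but say nothing about the contrast with wait-and-see.

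**4. Precision of a by-arm comparison**

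Half-width of the 95% interval for a risk difference, with equal true rate p and 190 per arm: 1.96 × √(2p(1−p)/190).

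- p = 1.6%: 1.96 × √(2 × 0.016 × 0.984/190) = 2.5 points.
- p = 5%: 1.96 × √(2 × 0.05 × 0.95/190) = 4.4 points.

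The 1.6% is the mortality after conservative treatment quoted in Section 1; the 5% is an assumption. Neither is a forecast for this trial.

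Power of a two-sided 5% test at 190 per arm: Φ{[Δ√n − 1.96√(2p̄(1−p̄))] / √(p₁(1−p₁) + p₂(1−p₂))}.

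| Rates (illustrative) | Power |
|---|---|
| 1% vs 2% | 12% |
| 1.6% vs 4.2% | 33% |
| 2% vs 5% | 36% |
| 5% vs 10% | 46% |
| 5% vs 15% | 90% |

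For 1.6% against 4.2%, 80% power would need about 1,306 patients. The 4.2% is the snapshot-study mortality after operative treatment of an obstruction and is not an expected rate for elective surgery.

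**The case against.** The strongest reply is that little is lost. Harm is recorded in both arms. Operative deaths would appear as Clavien-Dindo grade V, and every death is an SAE. Recurrence leading to surgery is an outcome in all patients. Quality of life is modelled, and the intention-to-treat economic evaluation sets QALYs and costs, including those of adverse events and readmissions, against each other by strategy. By-arm SAE tables are often left to the statistical analysis plan, which is not shown. With N set for recurrence, describing rare harms without a test is reasonable.

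Most of this stands. It shows that the data suffice, that part of the control-arm burden is covered, and that a formal test is not the remedy. It does not reconcile the comparative objective in Section 2 with the operative-group analysis in Section 8, or the outcomes in Section 1 with those in 6.1.2. Nor does a QALY difference replace a count of deaths and severe events in each arm.

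Four stronger readings are tempting, but the documents do not support them:

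- *The trial cannot answer its safety question.* It can, from the planned data; the stated analysis simply does not do so.
- *The operative group is an as-treated set that includes control cross-overs.* The term is undefined, and Sections 6.6 and 8 apply intention to treat. The definition is missing, but no as-treated analysis is stated.
- *Deaths are hidden by censoring.* Section 8 mentions censoring for loss to follow-up and, in the per-protocol analysis, for intercurrent events. It is silent on death.
- *SAEs are collected for only three months.* The sentence "The sponsor will report the SAEs occurring up to 3 months following treatment" governs onward reporting to the ethics committees; Section 7.3 runs to the end of the study.

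**Conclusion.** The concern holds as a mismatch between objective, endpoint list and analysis. As planned, the comparative safety part of the primary objective goes unanswered, and mortality is an outcome in one section and absent from those that should carry it. The defect lies in wording and stated analysis. It does not touch the data to be collected or the primary recurrence analysis.

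On the plan's figures, about 4 to 8 organ injuries stand against about 19 fewer recurrences, so harm is not negligible beside benefit. A by-arm estimate would be imprecise: about ±2.5 points at a 1.6% rate and ±4.4 points at 5%, with power between 12% and 46% for most contrasts tried. These figures assume 190 analysed per arm and rest on illustrative event rates.

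**What to change.** - In 6.1.2, restore all-cause mortality, and bring the Summary and Section 8 into line with Section 1.
- In 6.1.2 and 8, report mortality, SAEs, Clavien-Dindo grade IIIb or higher events, ICU admission and reintervention by randomised arm (intention to treat), from randomisation to 24 months in both arms, as risk differences with 95% confidence intervals. At low counts use an interval that does not rely on the simple normal approximation.
- State that this is estimation, that N was set for recurrence only, and that precision for rare events is limited.
- Fix two definitions in advance. A recurrence is an unplanned admission and so meets the SAE definition in 7.2.2; show SAEs with and without recurrence admissions. The Clavien-Dindo scale is worded for the post-operative course; say how it applies to events that do not follow study surgery.
- Keep the operative-group description as a supplement, and state whether it includes control patients who cross over.
- A sensitivity analysis of recurrence or death is optional.

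If no by-arm comparison is intended, reword the primary objective so that safety means a description of operative morbidity.

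The cost is an amendment of wording and a few tables. No further patients, visits or data items are needed.

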#### 4.4 Sample size calculation

Primary outcome is the time to recurrence measured at two years of prospective follow-up. We will perform a superiority trial. Based on previous literature, we expect 20% recurrence in 2-year with wait-and-see policy (based on a mix of patients with a first and recurrent episode of aSBO) and a 10% recurrence rate after intervention, resulting in a hazard ratio (HR) of approximately 0.47.

We estimated that if 378 patients were randomly assigned in a 1:1 ratio (i.e., 189 per group) to the intervention group or the control group, our study would have 80% power to detect an HR for recurrence of adhesive small bowel obstruction of approximately 0.47 at a two-sided  $\alpha$  level of 0.05. After rounding the total number of patients up, we aim to include a total of 380 patients. Analysis will be performed by intention to treat basis, using survival analysis. We will use cox regression to be able to apply multivariable analysis to account for covariates such as previous episodes of ASBO.

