## 6.1.3 Other study parameters (if applicable)

At baseline we will collect data on surgical history, co-morbidity, BMI, and substance use. During the surgery we will collect data on surgical approach, intraoperative events graded by Class-Intra, extent and location of adhesions (measured by Peritoneal Adhesion Index), Completeness of adhesiolysis, and use of barrier.

At the follow-up visits we will perform history taking and physical examination focused on identification of potential readmissions for ASBO at other hospitals, chronic complaints, and late surgical complications such as incisional hernia.

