## 7.2 AEs, SAEs and SUSARs

## 7.2.1 Adverse events (AEs)

Adverse events are defined as any undesirable experience occurring to a subject during the study, whether or not considered related to the intervention. All adverse events reported spontaneously by the subject or observed by the investigator or his staff will be recorded.

Adverse events related to adhesiolysis include complications associated with abdominal surgery such as wound infection, haemorrhage, pneumonia and thrombosis. Further adhesiolysis is associated with a small risk (2-4%) of iatrogenic injury to organs such as the bowel. In case of iatrogenic bowel injury, failure of healing of this injury can results in further negative sequelae including reoperation, stoma, and ICU admission.

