## 8.1 Primary study parameter(s)

The primary outcome, incidence of recurrence, is analyzed using survival analysis (Cox-regression) on intention to treat basis. The primary outcome is analysis in the total group, and in the subgroups of patients presenting with a first or recurrent episode of aSBO.

In previous studies, (amongst others: v.d. Beukel et al.) no indications have been found for 'violation' of the assumption for proportional hazards. Stratification is applied on the variables *first episode of aSBO vs. recurrent episode of aSBO*, and *hospital*. No other covariates will be taken into account. We will test two-sided.

After a new surgery for another reason, the risk for aSBO will increase as a consequence of new adhesions that can arise due to this surgical procedure. In this trial, we expect this to be a rare event, and the few times that this will happen, this will probably be spread evenly over the two groups. Therefore, there is no reason for censoring nor removal in the intention-to-treat protocol. Only in the secondary perprotocol analysis these patients will be removed.

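### Randomisation is given as the reason later non-aSBO surgery is balanced, but as worded that event includes reoperations caused by the trial adhesiolysis, so the secondary per-protocol analysis is tilted slightly towards surgery

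*Protocol*

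**What the plan says.** Section 8 names as the main intercurrent event any abdominal operation during follow-up whose indication is not aSBO. It expects this in about 5% of patients within two years, without a split by arm, and reasons: "Because of the randomization, we expect both groups to be at equally risk for such event". Section 8.1 repeats that "this will probably be spread evenly over the two groups" and uses this to justify neither censoring nor removing these patients in the intention-to-treat analysis. Section 8.1 also states that such surgery raises the risk of aSBO through new adhesions.

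The two sections treat these patients differently in the secondary per-protocol analysis: section 8 censors them, section 8.1 removes them.

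Elsewhere the protocol describes abdominal surgery that follows from the trial operation. Section 7.2.1 gives a 2-4% risk of iatrogenic organ injury and says "failure of healing of this injury can results in further negative sequelae including reoperation, stoma, and ICU admission". Section 6.1.2 collects 90-day reinterventions under morbidity of elective adhesiolysis. Section 6.1.3 looks for "late surgical complications such as incisional hernia" at follow-up.

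**The concern.** Randomisation equalises risk at baseline. It cannot equalise a later event that one of the allocated treatments can produce. Surgery for a leak or for bleeding after adhesiolysis is not done for aSBO, so it meets the definition in section 8, and neither section 8 nor 8.1 excludes it. Controls can reach the trial operation by the planned cross-over only after a recurrence (sections 3 and 6.3). Before a first recurrence, complications of that operation therefore belong essentially to the intervention arm.

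At stake is the per-protocol estimate of recurrence. It would selectively drop intervention patients whose operation was complicated, and by section 8.1's own reasoning these are patients at raised risk of the endpoint. In an open-label surgical trial, readers are likely to use that estimate as a check on the main result.

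**Working it through.** **1. The plan's own figure.** Inputs from section 4.4: "we expect 20% recurrence in 2-year with wait-and-see policy", 10% after intervention, 189 per group, and "our study would have 80% power to detect an HR for recurrence of adhesive small bowel obstruction of approximately 0.47". Alpha is 0.05 (section 8: "Differences with a P-value <0.05 are considered statistically significant"; section 8.1: "We will test two-sided").

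- HR = ln(0.90)/ln(0.80) = 0.472.
- Events by Schoenfeld's formula: 4 × (1.960 + 0.842)² / (ln 0.472)² = 55.75, so 56.
- Mean event probability (0.20 + 0.10)/2 = 0.15, so 56/0.15 = 373.3, or 374 patients against the stated 378.
- Power with 378 × 0.15 = 56.7 events is 80.7%.

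The stated size reproduces, and the present point does not change it.

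**2. How many patients meet the event.** With 190 per arm, the protocol's 5% is 0.05 × 190 = 9.5 patients per arm. Let the trial operation add a proportion x of reoperations in the intervention arm. The protocol gives no value for x. The calculation also assumes that these come on top of the 5%, which section 8 does not settle.

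| x (assumed) | Intervention | Control | Ratio |
|---|---|---|---|
| 1% | 11.4 | 9.5 | 1.2 |
| 2% | 13.3 | 9.5 | 1.4 |
| 4% | 17.1 | 9.5 | 1.8 |
| 6% | 20.9 | 9.5 | 2.2 |

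**3. Effect on the per-protocol HR.** Assume that the extra patients leave the analysis near time zero, so that censoring and removal coincide, that they have k times the recurrence hazard of the other intervention patients, and that the background 5% is neutral. Let r be the two-year risk in the remaining intervention patients. The planned 10% overall requires

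(1 − x)·r + x·[1 − (1 − r)^k] = 0.10,

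and the per-protocol HR is ln(1 − r)/ln(0.80).

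| x | k = 1 | k = 1.5 | k = 2 | k = 3 |
|---|---|---|---|---|
| 2% | 0.472 | 0.468 | 0.463 | 0.456 |
| 4% | 0.472 | 0.463 | 0.455 | 0.440 |
| 6% | 0.472 | 0.459 | 0.447 | 0.425 |

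Check for x = 4%, k = 3: r = 0.0935, and 0.96 × 0.0935 + 0.04 × (1 − 0.9065³) = 0.100.

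**4. Scale.** With 380 × 0.15 = 57 events, the standard error of the log HR is about √(4/57) = 0.26. The largest shift for x of 2-4% is ln(0.472/0.440) = 0.07, about a quarter of one standard error.

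**5. A limit on these figures.** They fit censoring at the time of surgery. Removal could also delete a control patient who recurred, crossed over and was then reoperated, and with that patient a recurrence. This works against surgery. Its ceiling, if all 0.20 × 190 = 38 recurring controls crossed over and 2-4% were reoperated, is 0.8-1.5 control recurrences. No cross-over rate is given, so this is left out above.

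**The case against.** The strongest reply is about meaning. The trial operation is itself done because of aSBO, and sections 6.1.2 and 7.2.1 file its reoperations as morbidity of adhesiolysis. The sponsor may therefore have meant only surgery unconnected with the trial, for which equal risk is a fair expectation. This reading is possible, but sections 8 and 8.1 do not state it, and one clause would settle the matter.

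Other limits stand in full:

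- A reader might infer that every exclusion is one-sided. It is not. Section 4.2 admits previously operated patients, section 5.1 allows for stomas and abdominal wall defects, and Table 1 examines both arms for incisional hernia. Hernia repair and stoma reversal can occur in controls, so only those that follow from the trial operation are one-sided. The background 5% leaves both arms.
- A reader might take 2-4% as a reoperation rate and conclude that 13-17 intervention patients would be dropped against 9-10 controls. Section 7.2.1 gives an injury rate and attaches reoperation only to injuries that fail to heal. Reoperation for bleeding or infection would add to that subset, but no rate is given for it. The counts are illustrative.
- A reader might infer that the primary result is biased. It is not. Intention to treat keeps these patients, which is right whether or not the event is balanced.
- Few recurrences are involved. With 3.8-7.6 extra patients, a 10% risk gives 0.4-0.8 recurrences. At three times the hazard (risk 1 − 0.9³ = 27%) it is about 1-2.

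**Conclusion.** The point holds for the secondary per-protocol analysis only. Randomisation is not a valid reason to expect balance in an event that, as defined, includes complications of one arm's operation. Under the rule as written, the per-protocol analysis with censoring drops complicated intervention patients selectively and moves towards surgery if, as section 8.1 holds, their aSBO risk is raised.

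The shift is small: from 0.472 to about 0.44-0.47 if 2-4% of the intervention arm are reoperated early with 1.5-3 times the hazard. It is nil if the hazard is not raised. The reoperation rate, the hazard multiple, the early timing and the addition to the 5% are all assumptions. The point is worth acting on because the direction of the bias is predictable and the correction is a matter of wording.

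**What to change.** In sections 8 and 8.1:

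1. Define the intercurrent event as abdominal surgery that is neither for aSBO nor for a complication of the trial adhesiolysis. State that reoperation, stoma reversal or hernia repair resulting from that operation counts as such a complication.
2. Keep patients with complication-related surgery in the per-protocol analysis, as part of the intervention.
3. Drop randomisation as the reason for equal risk. With the narrower definition, similar risk may be stated as an expectation to be checked.
4. Report all later abdominal surgery by arm and by reason.
5. Reconcile the two per-protocol rules by censoring at the time of the event in both sections. Removal selects patients on something that happens after the start of follow-up, and it discards recurrences that came first.

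The cost is a few sentences, plus recording the indication for later operations beyond the 90 days already covered by the reintervention outcome. The per-protocol estimate may come out slightly less favourable to surgery. The primary analysis and sample size stay as they are.
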